6.4 Patient numbering, treatment assignment or randomization

6.4.1 Patient numbering

Each patient is identified in the study by a Subject Number (Subject No.), that is assigned when the patient is first enrolled for screening and is retained as the primary identifier for the patient throughout his/her entire participation in the trial. The Subject No. consists of the Center Number (Center No.) (as assigned by Novartis to the investigative site) with a sequential patient number suffixed to it, so that each subject is numbered uniquely across

the entire database. Upon signing the informed consent form, the patient is assigned to the next sequential Subject No. available to the investigator.

6.4.2 Treatment assignment or randomization

The assignment of a patient to a cohort will be coordinated by the sponsor or designated CRO by inclusion fax when all inclusion and exclusion criteria are fulfilled. The C1D1 visit should occur within 3 days after sending the fax.

If one of the cohorts reaches the planned patient number, the inclusion of new patients in this cohort will be stopped and all investigators will be informed accordingly.

6.4.3 Treatment blinding

This is an open label study.

6.5 Study drug preparation and dispensation

Patients will be provided with an adequate supply of study drug for self-administration at home, including instructions for administration, until at least their next scheduled study visit. Patients will receive ribociclib on an outpatient basis. The investigator shall provide the patient with instructions for ribociclib administration according to the protocol.

Letrozole and goserelin should be dispensed according to the local prescribing information and practice.

The investigator or responsible site personnel must instruct the patient or caregiver to take the study drugs as per protocol. Study drug(s) will be dispensed to the patient by authorized site personnel only. All dosages prescribed to the patient and all dose changes during the study must be recorded on the Dosage Administration Record CRF.

All study drugs will be provided by Novartis to the participating sites for all patients enrolled in this study until approval of Ribociclib (see [Table 6-1](#)) and will be dispensed by the study center personnel on an outpatient basis. For these patients study drugs will be provided by Novartis throughout the study. After ribociclib is commercially available, the investigator will prescribe all drugs according to the label to all patients who will be enrolled after commercial approval.

All dosages prescribed to the patient and all dose changes during the study must be recorded on the Dosage Administration Record eCRF.

Table 6-7 Preparation and dispensing

Study drugs	Dispensing	Preparation
Ribociclib	Tablets including instructions for administration are dispensed by study personnel on an outpatient basis.	Not applicable
Letrozole		
Goserelin	Monthly subcutaneous implant	Refer to local product information

6.5.1 Study drug packaging and labeling

Ribociclib is formulated as tablets of 200 mg strength for oral administration. Commercially available ribociclib will be supplied as tablets of 200 mg strength for oral administration in

blisters. Complete guidelines for management and administration of letrozole and goserelin can be found in the package insert. Ribociclib study medication will be packaged into bottles or blisters. The bottles should be opened only at the time of administration, as the drug is hygroscopic and light sensitive. All bottles will conform to all local regulatory requirements.

6.5.2 Drug supply and storage

Study treatments must be received by designated personnel at the study site, handled and stored safely and properly, and kept in a secured location to which only the investigator and designated site personnel have access. Upon receipt, the *study treatment* should be stored according to the instructions specified on the drug labels and according to instructions in the Investigator's Brochure.

Storage conditions for ribociclib, letrozole and goserelin will be described on the medication label/local package insert. The study drug should be stored in a secure, locked area while under the responsibility of the investigator. An authorized person at the investigator's site throughout the entire study must record receipt and dispensing of supplied study drugs.

As long as the study drugs are supplied by Novartis, they are to be stored between 2°C and 25°C and protect from moisture. The storage temperature must be recorded daily (except weekends and bank holidays) in the temperature log.

6.5.3 Study drug compliance and accountability

6.5.3.1 Study drug compliance

The investigator and/or study personnel will assess compliance at each patient visit. To accurately determine the patient's drug exposure throughout the study, the following information must be reported on the Drug Administration Record CRF for ribociclib, letrozole and goserelin pages and in the source document.

- Planned dose administration
- Actual total daily dose administered
- Start and end date of drug administration
- Dose change (no or yes)
- Reason for dose change (e.g. adverse event, dosing error, lab test abnormality etc.).

6.5.3.2 Study drug accountability

The investigator or designee must maintain an accurate record of the shipment of study drugs supplied by Novartis as well as of the prescriptions of ribociclib, letrozole and goserelin after ribociclib becomes commercially available. The investigator will be advised to document the dispensing and return of ribociclib, letrozole and goserelin throughout the entire study in a drug accountability log. The field monitor will review drug accountability during site visits and at the completion of the study. The patient will be advised to complete a study drug diary and present the bottles or blisters at the subsequent study visits and at the time of study drug discontinuation to review compliance and allow the investigator to document in the patient file and complete a drug accountability check.

The patient diary is not regarded as study documentation but is regarded as aid for discussions between investigator and patient.

Patients will be asked to return all unused Novartis-supplied study drugs and packaging on an ongoing basis or at the time of study drug discontinuation.

6.5.3.3 Handling of other study treatment

Not applicable.

6.5.4 Disposal and destruction

The drug supply should be destroyed at the local Novartis facility, Drug Supply group or third party, as appropriate. Destruction at the site is allowed only if permitted by local regulations and authorized by Novartis.

6.6 Study drug discontinuation

Study drug interruption refers to a patient stopping either study drug during the course of the study, but then re-starting it at a later time in the study. If one of the study drugs is discontinued, the other must be discontinued as well. If the study drug ribociclib or letrozole is interrupted for more than 4 weeks, the patient will be permanently discontinued from the study treatment.

All study drug interruptions must be recorded on the appropriate Dosage Administration CRF.

Patients whose ribociclib treatment is interrupted due to an adverse event or abnormal laboratory value must be followed at least once a week for 28 days and subsequently at 28 day intervals, until resolution or stabilization of the event, whichever comes first.

Study drug discontinuation refers to a patient's withdrawal from ribociclib. The reason for discontinuation from treatment must be recorded on the End of treatment CRF.

Patients may be withdrawn from the study treatment if any of the following occur:

- Adverse Event (including, but not limited to QTcF \geq 501 msec, confirmed at repeated ECG measurements and recurrent after dose adjustment was performed; Documented episode of ventricular tachycardia, or ventricular fibrillation; Complete heart block (Grade III AV block) or Second degree AV block Mobitz type II).
- Physician decision
- Progressive Disease
- Protocol deviation
- Study terminated by sponsor
- Adjustments to study treatment that result in discontinuation.
- Use of prohibited medication. Please refer to Section 6.3.3.

Patients who discontinue ribociclib $>$ 28 days should be scheduled for an End of Treatment Visit, whenever possible, after discontinuing ribociclib, at which time all of the assessments listed for the End of Treatment Visit (EoT) will be performed. The complete End of Treatment eCRF documentation should be done within one week. If ribociclib is permanently discontinued, the patient will be considered to have completed study treatment. All patients must have safety evaluations for 30 days after the last dose of study drug. AEs/SAEs with a suspected causality to study treatment must be reported beyond this 30 day safety interval.

Patients who discontinue study treatment should NOT be considered withdrawn from the study. They should return for the assessments indicated in Section 7-1. If they fail to return

for these assessments for unknown reasons, every effort (e.g. telephone, email, letter) should be made to contact them.

7 Visit schedule and assessments

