6.2.1.1 Ribociclib

Recommendations for dose reduction, interruption or discontinuation of ribociclib in the management of study drug related adverse reactions are summarized in [Table 6-3](#), [Table 6-4](#), [Table 6-5](#) and [Table 6-6](#).

Clinical judgment of the treating physician should guide the management plan of each patient based on individual benefit/risk assessment. However, for events requiring a discontinuation in [Table 6-3](#), [Table 6-4](#), [Table 6-5](#) and [Table 6-6](#) or listed in Section 7.1, treatment must be discontinued.

If a patient inadvertently doses ribociclib on a rest day (e.g. days 22-28 of any given cycle), ribociclib should be interrupted to ensure 7 consecutive rest days and avoid overdose. The visit schedule will not be adjusted.

Table 6-3 Ribociclib dose adjustment and management recommendations for hematological adverse reactions

Toxicity/Grade	Dose Adjustment and Management Recommendations
Thrombocytopenia	
Grade 1($\geq 75 \times 10^9/L$)	No dose adjustment required.
Grade 2 ($\geq 50 \times 10^9/L - < 75 \times 10^9/L$)	Dose interruption until recovery to grade ≤ 1 . Re-initiate ribociclib at the same dose.
Grade 3 ($\geq 25 \times 10^9/L - < 50 \times 10^9/L$)	Dose interruption until recovery to grade ≤ 1 . Re-initiate ribociclib at the same dose level. If toxicity recurs at grade 3: temporary dose interruption until recovery to grade ≤ 1 and reduce ribociclib to the next lower dose level.
Grade 4($< 25 \times 10^9/L$)	Dose interruption until recovery to grade ≤ 1 . Re-initiate ribociclib at the next lower dose level. If toxicity recurs at grade 4: discontinue ribociclib
Absolute neutrophil count (ANC),	
Grade 1 ($\geq 1.5 \times 10^9/L$)	No dose adjustment required.
Grade 2 ($\geq 1.0 - < 1.5 \times 10^9/L$)	No dose adjustment required.

Toxicity/Grade	Dose Adjustment and Management Recommendations

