6.2.1.3 Additional follow-up for QTc prolongation

Table 6-5 Ribociclib dose adjustment and management recommendation for QTc prolongation (CTC AE v4.03)

Grade	Dose Modification
For All Grades	
1. Check the quality of the ECG and the QT value and repeat if needed.2. Perform analysis of serum electrolytes (K+, Ca++, Phos, Mg++). If outside of the normal range, interrupt ribociclib administration, correct with supplements or appropriate therapy as soon as possible, and repeat electrolytes until documented as normal.3. Review concomitant medication usage for the potential to inhibit CYP3A4 and/or to prolong the QT interval.4. Check compliance with correct dose and administration of ribociclib. 
Consider collecting a time matched PK sample; record date and time of last study drug intake.

1 QTcF 450-480 ms	Perform steps 1-4 as directed in "For All Grades". No dose adjustment required.
2 QTcF 481-500 ms	
Interrupt ribociclib. Perform steps 1-4 as directed in "For All Grades."
 
Perform a repeat ECG within one hour of the first QTcF of ≥ 481 ms. Repeat ECG as clinically indicated until the QTcF returns to < 481 ms, restart LEE011 with dose reduced by 1 dose level.
 
If QTcF ≥ 481 ms recurs, ribociclib should be reduced by 1 dose level. Repeat ECGs 7 days and 14 days after dose resumption (then as clinically indicated) for any patients who had therapy interrupted due to QTcF ≥ 481 ms.

3 QTcF ≥ 501 ms on at least two separate ECGs	
Interrupt ribociclib. Perform steps 1-4 as directed in "For All Grades."
 
Transmit ECG immediately and confirm prolongation/abnormalities.
 
Perform a repeat ECG within one hour of the first QTcF of ≥ 501 ms.
 
If QTcF remains ≥ 501 ms, consult with a cardiologist (or qualified specialist) and repeat cardiac monitoring as indicated until the QTcF returns to < 481 ms.
 
If QTcF returns to < 481 ms, ribociclib will be reduced by 1 dose level.
 
If QTcF remains ≥ 481 ms after performing steps 1-4 as directed in "For All Grades," discontinue LEE011.
 
Repeat ECGs 7 days and 14 days after dose resumption (then as clinically indicated) for any patients who had therapy interrupted due to QTcF ≥ 501 ms.
 
If QTcF of ≥ 501 ms recurs, discontinue ribociclib.

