7.1.3.2 Criteria for premature patient withdrawal

Patients may voluntarily withdraw from the study or be dropped from it at the discretion of the investigator at any time.

Patients must be withdrawn from the study treatment if any of the following occur:

- Pregnancy
- Subject decision
- Lost to follow up

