Medications with a known risk for QT prolongation ⁴	Amiodarone, anagrelide, arsenic trioxide, astemizole, azithromycin, bepridil, chloroquine, cocaine, chlorpromazine, cilostazol, ciprofloxacin, cisapride, citalopram, clarithromycin, disopyramide, dofetilide, domperidone, donepezil, dronedarone, droperidol, erythromycin, escitalopram, flecainide, fluconazole, gatifloxacin, grepafloxacin, halofantrine, haloperidol, ibutilide, levofloxacin, levomepromazine, levosulpiride, levomethadyl, mesoridazine, methadone, moxifloxacin, ondansetron, oxaliplatin, papaverine HCl (intracoronary), pentamidine, pimozide, probucol, procainamide, propofol, quinidiner, roxithromycin, sevoflurane, sotalol, sparfloxacin, sulpiride, sultopride, terlipressin, terodilene, terfenadine, thioridazine, vandetanib
Herbal preparations/medications	Herbal preparations/medications known as strong inducers or inhibitors of CYP3A4/5 or those with a known risk of QT prolongation are prohibited throughout the study. These herbal medications include, but are not limited to: St. John's wort, Kava, ephedra (ma huang), gingko biloba, dehydroepiandrosterone (DHEA), yohimbe, saw palmetto, and ginseng. Patients should stop using these herbal medications 7 days prior to first dose of study drug.

Category	Drug Name
Other investigational and antineoplastic therapies	Other investigational therapies must not be used while the patient is on the study. Anticancer therapy (chemotherapy, biologic or radiation therapy, except for palliative radiotherapy as outlined in the protocol , and surgery) other than the study treatments must not be given while the patient is on the study medication. If such agents are required then the patient must discontinue study drug.

¹ NTI = narrow therapeutic index drugs whose exposure-response indicates that increases in their exposure levels by the concomitant use of potent inhibitors may lead to serious safety concerns (e.g., Torsades de Pointes) or drugs which have <2-fold difference in the minimum toxic concentrations and minimum effective concentrations in the blood...

² Herbal product

³ P-gp inducer

⁴ Source: www.qtdrugs.org (as of Apr 7, 2015)

⁵ Drug has warning for risk of hepatotoxicity.

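### Protocol 6.6 makes stopping for recurrent QTcF of 501 ms or more optional, while Table 6-5 read with 6.2.1.1 makes it mandatory

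*Protocol*

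**What the plan says.** Section 6.6 of the protocol lists reasons for stopping study treatment under the sentence "Patients may be withdrawn from the study treatment if any of the following occur". Its adverse-event bullet names a QTcF of at least 501 msec, "confirmed at repeated ECG measurements and recurrent after dose adjustment was performed; Documented episode of ventricular tachycardia, or ventricular fibrillation", and then high-grade AV block. A later bullet reads "Use of prohibited medication. Please refer to Section 6.3.3".

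Section 6.2.1.1 begins with discretion: "Clinical judgment of the treating physician should guide the management plan of each patient based on individual benefit/risk assessment". The next sentence withdraws that discretion for events that require discontinuation in Tables 6-3 to 6-6 "or listed in Section 7.1, treatment must be discontinued".

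Table 6-5 (Section 6.2.1.3) gives the QT rules. In the grade 3 row, once the dose has been reduced, the instruction is that if a QTcF of 501 or more "ms recurs, discontinue ribociclib". The grade 4 row also ends in discontinuation. It applies when a QT criterion (501 or more, or a rise of more than 60 ms from baseline) occurs together with torsades, polymorphic ventricular tachycardia or evidence of serious arrhythmia.

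In Appendix 14.1, the Table 14-1 row on other investigational and antineoplastic therapies states: "If such agents are required then the patient must discontinue study drug".

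Section 7.1.3.2 has its own list, introduced by "Patients must be withdrawn from the study treatment if any of the following occur". It covers pregnancy, subject decision and loss to follow-up.

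**The concern.** An investigator whose patient has a second QTcF of 501 ms or more after a dose reduction finds *may* in one section and *must* in another. QT prolongation is one of the important identified risks named in Section 1.2.6, so the stopping rule for it should have a single reading.

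There is also a reporting consequence. Section 12 requires significant protocol deviations to be recorded and reported in the study report. Under 6.2.1.1 and Table 6-5, continued dosing after the recurrence is a departure from the protocol; under 6.6 alone it is allowed. Two sites could act identically and be classified differently.

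**Working it through.** No sample size, power or other planned figure is involved. The check compares the passages event by event.

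| Event | Status in 6.6 | Status elsewhere | Overlap |
|---|---|---|---|
| QTcF of 501 ms or more, confirmed, recurring after dose adjustment | *may* | Discontinue (Table 6-5, grade 3), made mandatory by 6.2.1.1 | Essentially complete |
| Ventricular tachycardia | *may*, any documented episode | Discontinue (Table 6-5, grade 4), only with the QT criterion; made mandatory by 6.2.1.1 | Partial |
| Prohibited medication | *may*, pointing to 6.3.3 | *must* in Table 14-1, investigational and antineoplastic row only | Partial |
| High-grade AV block | *may* | Not named in Table 6-5 | No conflict shown |

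1. Recurrent QTcF. Section 6.6 asks for three things: 501 ms or more, confirmation on repeat ECG, and recurrence after a dose adjustment. Table 6-5 grade 3 asks for 501 ms or more on at least two ECGs, followed by interruption and a dose reduction, and then recurrence. These describe the same patient. The table titles speak of recommendations, but the second sentence quoted from 6.2.1.1 makes their discontinuation entries binding.

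2. Ventricular tachycardia. Grade 4 needs both the QT criterion and the arrhythmia. The two sections meet only where a tachycardia covered by grade 4 comes with the QT criterion.

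3. Prohibited medication. Section 6.3.3 includes other investigational and antineoplastic therapies, and Table 14-1 makes discontinuation mandatory when these are required. For drugs with a known torsades risk, Section 6.3.4 requires interruption, which is a different action.

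4. Size. The documents give no rate for a recurrent QTcF of 501 ms or more. The closest figure is in Section 1.2.6: 11 of 334 patients (3.3%) on ribociclib plus letrozole had a new QTcF above 480 ms. Applied to this trial, 11/334 × 500 = 16.5, or about 17 patients. The event at issue also needs 501 ms or more and recurrence after a dose adjustment. If the pivotal rate carries over, the range is 0 to about 17.

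   Section 1.2.1.2.1 gives a second figure: 4 single-agent patients at 600 mg (5.4%) reached 500 ms or more, and 0.054 × 500 = 27. It rests on four patients, comes from single-agent use, uses a 500 ms cut-off and says nothing about recurrence. It is neither a good estimate nor an upper bound for this event.

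**The case against.** The strongest defence is that 6.6 catalogues possible withdrawal reasons and grants no discretion. The same *may* covers termination by the sponsor and adjustments to treatment that end in discontinuation, neither of which works as an investigator's option. Section 4.2 of Appendix 14.2 likewise uses *may* for a list that includes pregnancy and loss to follow-up, which 7.1.3.2 makes mandatory. An investigator is also sent to Table 6-5 from elsewhere: the text under Table 7-4 requires interruption at an average QTcF of 481 ms or more and refers to that table.

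This makes a deliberate grant of discretion unlikely, but it does not remove the conflict. Section 7.1.3.2 opens with the same sentence as 6.6 except that it says *must*, so a site comparing the two lists could fairly take the difference as intended. Section 6.6 does not refer to Table 6-5, and its QTcF bullet restates the threshold and the recurrence condition closely enough to read as a rule.

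Three parts of the defence stand in full:

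- A reader might infer that every cardiac event and every prohibited drug in 6.6 is mandatory elsewhere. The documents do not support this. AV block has no mandatory counterpart among the passages compared, ventricular arrhythmia without the QT criterion is outside grade 4, and 6.3.4 requires only interruption for drugs with a known torsades risk.
- A reader might infer that the pointer to Section 7.1 in 6.2.1.1 is an error because 7.1.3.2 omits these events. The pointer is additive: it covers table events *or* events listed in 7.1. Section 7.1 has its own mandatory list, which need not repeat the tables.
- A reader might infer that analysis results depend on the answer. Section 8.1.1 records the action taken for each adverse event as it happened, and Table 1 in SAP Section 5.8 has no per-protocol exclusion for continued dosing after a QT event (D_01 concerns interruptions of more than 28 days).

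**Conclusion.** The inconsistency is real. It is complete for one event, a confirmed QTcF of 501 ms or more that recurs after dose adjustment. It is partial for two others: ventricular tachycardia that meets the grade 4 QT criterion, and required investigational or antineoplastic therapy. It is not shown for the remaining events in 6.6.

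It bears on patient safety and on how deviations are classified. The clinical benefit rate, the analysis-set definitions and the other efficacy results do not change. The number of patients is unknown and probably small. The ceiling of about 17 of 500 assumes that the pivotal trial's 3.3% applies to this broader population, and it counts every new value above 480 ms as if it had reached 501 ms and recurred.

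Enrolment was complete at Amendment 4. For patients still on treatment the rule is live; for the others the value lies in consistent deviation classification. The point is worth correcting because it concerns a safety rule and is cheap to settle.

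**What to change.** Reconcile Sections 6.2.1.1 and 6.6, the grade 3 and grade 4 rows of Table 6-5, and the investigational and antineoplastic row of Table 14-1, so that each overlapping event has one stated status, mandatory or discretionary. One way is for 6.6 to defer explicitly, for these events, to whichever rule the sponsor confirms. The clinical choice belongs to the sponsor. No change to the Section 7.1 pointer is called for on this evidence.

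The confirmed status should also be used when classifying continued dosing after such an event as a deviation or not. The cost is a clarification letter or amendment wording; no analysis has to be changed or rerun.
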